CASTomize Pilot Study Protocol

Principle investigator: [name]

Co-investigator: [name], [name]

Industrial collaborator: [name], [name], [name]

CASTomize pilot study protocol: a randomized controlled trial comparing CASTomize 4D printed cast versus standard of care fiberglass cast on fracture reduction and patient reported outcomes.

Abstract

Background: For many years, traditional fibreglass casting has been the gold standard of immobilisation for distal radius fractures (DRFs). However, the traditional method of casting has obvious disadvantages such as poor patient comfort, inability to be in contact with water, difficulty observing skin underneath and requiring multiple cast changes in the patients care journey. This study compares the Castomize 4D printed casts versus the conventional fiberglass cast in fracture immobilisation, and various patient reported outcomes.

Methods/design: This study is a randomised control trial comparing Castomize 4D printed cast versus conventional fibreglass casts in isolated conservatively treated distal radius fractures. The primary outcome measure is fracture reduction. Secondary outcome measures include patient reported outcome measures such as the Adult Rated Cast Evaluation Questionnaire (ARCEQ)[1][2], comfort of the cast, quality of life assessed with the EQ-5D-5L questionnaire[3], cost-effectiveness and adverse events occurrence. In total, 30 patients will be included and followed for 6 months.

Trial registration: Pending

Registration number: Pending

Background

Displaced distal radius fractures (DRF) are very common in the adult population and their incidence is still on rising trend due to aging population. This is an issue which is pervasive across all ages, but most common in the elderly. In 2019, 180 million fractures happened worldwide. An average of 5 fracture incidents occurs every second. The current gold standard in fracture immobilisation is via the application of a fibreglass cast. However, the current fibreglass cast has multiple disadvantages. The cast is bulky, has poor ventilation and cannot come into contact with water. This gives patients considerable discomfort, and are unable to bathe and provide hygiene to their injured limb for the duration of the casting. Because the cast is not breathable, skin maceration, itchiness and wounds

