may become an issue. In this light, multiple casts changes become necessary to reduce the risk of soft tissue complications and to provide patient comfort. This increases the wastage of materials for the fibreglass casting as well as increases healthcare burden for the cast changes.

Castomize has created a 4D printed cast with its proprietary materials and designs aimed at overcoming the challenges in the traditional casting methods. Its 4D printed casts are lightweight and breathable, allowing contact with water and hygiene. Its design facilitates visualisation of the skin and soft tissue conditions. It is also remouldable, potentially only requiring one device for the duration of the patients care journey.

The design of the 4D printed cast was done in collaboration with orthopaedic clinicians, prosthetists and senior casting technicians optimised for clinical use. A biomechanical test was performed to evaluate the biomechanical properties of the 4D printed cast in comparison to the conventional fibreglass casts and were found to be less stiff and with a lower load to failure. This was however accessed to be not clinically significant.

Therefore, this study aims to compares the Castomize 4D printed casts versus the conventional fiberglass cast in fracture immobilisation and various patient reported outcomes.

Methods/design

This manuscript is written according to the Consolidated Standards for Reporting Trials (CONSORT statement) and Standard Protocol Items: Recommendations for Interventional Trials (SPIRIT guidelines).

Objectives

The primary aim of the study is to assess non inferiority of the Castomize 4D printed cast versus conventional fibreglass casts in fracture immobilisation and reduction.

The secondary aim of the study is to assess differences in patient reported outcomes measures (ARCEQ, comfort of the cast, EQ-5D-5L, cost-effectiveness and adverse events occurrence) in the Castomize 4D printed cast versus conventional fibreglass casts.

Design, participants, interventions and outcomes

Study design and randomization

A randomised controlled trial will be conducted in a single institution: TTSRH.

Patients will be recruited at the outpatient clinic. Patients who meet the inclusion and exclusion criteria will be recruited and randomised into 2 groups. Randomisation will be carried out via block randomisation via a computer generated randomization sequence.

Group 1: Castomize 4D printed cast (Figure 2)

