Analgesic use		✓	✓	✓	✓	✓
EQ 5D5L		✓***		✓	✓	✓
ARCEQ				✓	✓	✓
MCQ- iMTA				✓	✓	✓

PCQ- iMTA				✓	✓	✓
-----------	--	--	--	---	---	---

*X-rays before and after reduction (obtained from standard of care results if available)

**ROM, grip strength done by study team. ROM, DRUJ and Kapandji will be collected as part of standard of care if available

*** EQ 5D5L status pre-fracture and post-fracture sustainment

Table 2 Baseline characteristics

Baseline characteristics	
Date of emergency room visit	Sex
Affected wrist	Date of Birth
Method of reduction	
	Hand dominance
	Mechanisms of injury
	Smoking Status
	General medical history
	Previous injuries of the affected extremity
	La Fontaine criteria

Outcome

Primary outcome The primary outcome of this study is the occurrence of fracture displacement assessed on PA and lateral radiographs at 1, 2 and 6 weeks. Displacement of the radius is defined by: As compared to the post reduction radiograph at T0, Displacement of : > 15° of dorsal angulation, > 20° of volar angulation, < 15° of radial inclination, > 3mm of radial shortening and > 2mm intraarticular step-off or gap. Measurements will be on standard PA and lateral radiographs of the wrist by trained members of the research team.

Secondary outcomes An overview of measurements is shown in Table 1.

- Comfort of the cast assessed via pictorial representation of pressure marks or areas of discomfort.
- Severity of pain evaluated with the Visual analogue Score (VAS)
- Patient will describe their average wrist symptoms over the past week on a scale of 0-10 using Adult Rated Cast Evaluation Questionnaire (ARCEQ) [6][7].
- Quality of life will be assessed using the 5-level EuroQol (EQ-5D-5L) scoring questionnaire.
- Cost-effectiveness will be measured using the Medical Consumption Questionnaire (iMCQ) and the Production Consumption Questionnaire (iPCQ) [8].
- Physical examination:
 - Range of motion (ROM) of the wrist will be measured with a goniometer. ROM concerns dorsal flexion, volar flexion, radial deviation, ulnar deviation, pronation and supination.
 - Grip strength will be measured with a Jamar hydraulic hand dynamometer. The maximum score for each side over 3 attempts will be used
 - Specific testing of the wrist and hand will be performed namely:
 - distal radioulnar joint (DRUJ) stability tested with the DRUJ ballottement test

- opposition of the thumb using the Kapandji score

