Both cost-effectiveness (CEA) and cost-utility (CUA) analysis will be performed from a societal perspective. For the calculation of medical costs, we will use charges as published in Singapore guidelines as a proxy of real costs. The unit per price of the cast application in patients with DRF will be calculated with the microcosting method. Intramural costs (i.a. additional diagnostics, number of hospital visits, in case of hospital admission the length of stay etc.) are collected from the electronic health record. Productivity costs will be registered in detail by the iPCQ. The iMCQ and the iPCQ are validated by the Institute of Medical Technology Assessment (Erasmus University, Rotterdam, The Netherlands).

The difference in costs and effects of CASTomize instead of a circumferential cast will be calculated as incremental cost-effectiveness ratio (ICER). The primary effect outcome measures will be the number of re-displacements for the CEA and quality-adjusted life years (QALY) for the CUA. QALYs will be measured, based on the Singaporean tariff for the EQ-5D-5L.

The sensitivity analysis will assess the robustness of the results to changes in costs and effect parameters. Bootstrapping with 1000 replications will be used to estimate 95% confidence intervals around cost differences and the uncertainty surrounding the ICERs. This will be graphically presented on cost-effectiveness planes and acceptability curves using the net benefit framework. For the time horizon of 6 months, discounting is not necessary.

Data management

All data are handled confidentially and anonymized in compliance with the Singapore Personal Data Protection Act (PDPA). Personal data of participants will be changed by a study number. This number is used for all study documentation, study reports and publications. The key of this study number will be handled by an independent researcher. During the study period, all data will be collected and managed using GemsTracker electronic data capture tools. Paper case report forms are entered in GemsTracker by the researcher and the original paper case forms will be filed in the investigator site file at the recruiting hospital. All data is stored for 10 years.

Data monitoring

Since the study is labelled as low risk, a data safety monitoring board is not required.

References

- [1] M. Neubauer, "DASH Score," *Heartbeat Medical*, Jul. 22, 2021. <https://heartbeat-med.com/resources/dash-score/> (accessed Nov. 06, 2022).

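### No adjustment of QALYs for pre-fracture EQ-5D-5L is specified, although the score is scheduled; with 30 patients, chance imbalance can match or exceed a QALY effect confined to the casting weeks

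*Combined protocol and SAP*

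**What the plan says.** The section on cost-effectiveness analysis plans a cost-utility analysis with "quality-adjusted life years (QALY) for the CUA" as the effect measure. On their derivation it says "QALYs will be measured, based on the Singaporean tariff for the EQ-5D-5L". Differences in costs and effects are combined in an ICER, and "Bootstrapping with 1000 replications will be used to estimate 95% confidence intervals around cost differences and the uncertainty surrounding the ICERs". The horizon is stated in "For the time horizon of 6 months, discounting is not necessary". The section gives no regression model, covariate or area-under-the-curve rule for QALYs, and does not say whether they will be adjusted.

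The EQ-5D-5L row of Table 1 has no tick at T0. Its T1 cell carries a footnote, "EQ 5D5L status pre-fracture and post-fracture sustainment", so the pre-fracture state is asked about a week after inclusion (D7 ± 3). The only covariates named in the plan (age, osteoporosis and fracture characteristics) belong to the primary outcome. EQ-5D-5L scores also enter a linear mixed model over T0-T5 under the secondary outcomes. That analysis names no covariates and does not define the QALY difference used in the ICER.

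On size, the abstract says "In total, 30 patients will be included and followed for 6 months". Under study design, patients are "recruited and randomised into 2 groups" by block randomisation, with no allocation ratio and no stratification stated.

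**The concern.** Part of a patient's utility over six months reflects health before the fracture. Eligibility starts at age 21 with no upper limit and general health is not restricted, so that component may vary widely. In a trial of this size randomisation will often leave the arms somewhat different on it.

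The advantages the background claims for the printed cast (comfort, contact with water, hygiene) apply while it is worn. Comfort is measured only at T1-T3. A benefit confined to those weeks is a small QALY quantity, and a modest chance difference in pre-injury health over the full horizon can be as large. The realised imbalance would then move the point estimate, the ICER and the position on the cost-effectiveness plane. Leaving adjustment unspecified also leaves the choice open until the data have been seen.

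**Working it through.** The documents give no utility SD, correlation, expected QALY effect or sample-size calculation, so there is no figure of the plan's own to reproduce.

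**Inputs from the documents.** 30 patients in two groups. Horizon 6 months (T5 at D168). T3 is called 6 weeks in the text and D35 ± 7 in Table 1, hence 35-42 days as the casting period; no cast duration is stated, so this is an inference.

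**Assumed inputs.** 1:1 allocation, n = 15 per arm. SD of pre-fracture utility 0.10-0.20. Slope b of follow-up on pre-fracture utility 0.3-0.7. Cast effect 0.02-0.10 utility while the cast is on.

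**Step 1: imbalance carried into QALYs.** SE = SD × √(2/15) × b × 168/365.25, where √(2/15) = 0.365 and 168/365.25 = 0.46.

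| SD | b = 0.3 | b = 0.7 |
|---|---|---|
| 0.05 | 0.0025 | 0.0059 |
| 0.10 | 0.0050 | 0.0118 |
| 0.20 | 0.0101 | 0.0235 |

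The SD 0.05 row shows a more homogeneous population than the assumed range.

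**Step 2: effect confined to casting.** 0.02 × 35/365.25 = 0.0019; 0.10 × 42/365.25 = 0.0115 QALY.

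**Step 3: how often imbalance alone exceeds an effect.** P = 2 × [1 − Φ(effect/SE)]. Here the horizon is 0.5 year. At SD 0.15 and b = 0.5, SE = 0.15 × 0.365 × 0.5 × 0.5 = 0.0137.

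| Assumed effect | QALY | P, SD 0.15 and b 0.5 | P, SD 0.10-0.20 and b 0.3-0.7 |
|---|---|---|---|
| 0.05 for 6 weeks | 0.006 | 67% | 29-82% |
| 0.10 for 6 weeks | 0.012 | 40% | 4-65% |
| 0.20 for 6 weeks | 0.023 | 9% | <1-37% |
| 0.05 for 26 weeks | 0.025 | 7% | <1-33% |
| 0.10 for 26 weeks | 0.050 | <1% | <1-5% |

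With 168 days in place of 0.5 year, the SE in the middle column is 0.0126 and its first two probabilities become 65% and 36%.

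**Step 4: what adjustment gains.** The SE of the QALY difference is multiplied by √(1 − ρ²), where ρ is the correlation of QALY with pre-fracture utility (the one degree of freedom spent is ignored). With an assumed QALY SD of 0.06, the unadjusted 95% half-width is 1.96 × 0.06 × 0.365 = 0.043.

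| ρ | SE factor | Half-width | Power for 0.0115 QALY |
|---|---|---|---|
| none | 1 | 0.043 | 8% |
| 0.3 | 0.95 | 0.041 | 8% |
| 0.5 | 0.87 | 0.037 | 9% |
| 0.7 | 0.71 | 0.031 | 11% |

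**Consistency check.** Slope and correlation are tied by ρ = 0.46 × b × SD / SD of QALY. At SD 0.15, b = 0.5 and QALY SD 0.06, ρ = 0.0345/0.06 = 0.58, inside the assumed range. At SD 0.20 and b = 0.7 the numerator is 0.064, so the upper end of Step 1 requires a QALY SD above 0.064.

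**The case against.** The strongest case is that randomisation already deals with this. The unadjusted difference is unbiased over repeated allocation, and resampling patients carries their utility variation into the plane and the acceptability curve. That stands: imbalance appears as uncertainty and is not simply mistaken for a cast effect. What remains is lost precision and a shifted estimate in the one sample obtained.

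A second objection is that the covariate, as scheduled, is unsafe. It is recalled at T1, after allocation and about a week in the cast, and no blinding is described. Recall could differ by arm, and adjusting for it could introduce a bias that the unadjusted comparison lacks. This stands too, and it is why the timing should change along with the model.

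A third is that a cast effect need not end with the cast. If the casts differ in re-displacement or conversion to surgery, utility could differ for months. Step 3 bears this out: an effect of 0.050 QALY would be exceeded in at most 5% of trials over the range shown. A reader might infer that imbalance outweighs any plausible cast effect. The documents do not support that, and the ranges in Steps 1 and 2 overlap.

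Two further inferences should be resisted. The plan does not choose a raw arm difference; it is silent. Nor can it be said that no analysis uses the pre-fracture score: the mixed model refers to a baseline, and with no EQ-5D-5L at T0, the T1 cell is the only candidate for it.

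**Conclusion.** The concern holds as a gap in specification with a modest, inexpensive remedy. No baseline-utility adjustment is specified for QALYs although the plan schedules the score. Under the assumed SD of 0.10-0.20 and slope of 0.3-0.7, the imbalance standard error of 0.005-0.024 QALY is of the same order as, or larger than, the 0.002-0.012 QALY from an effect limited to casting. If the SD were only 0.05, it would fall below the upper end of that effect. Every SD, slope and effect size is an assumption, and 15 per arm assumes equal allocation.

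Adjustment would cut the standard error by about 5-29% for ρ of 0.3-0.7. It would not make the comparison informative: at a QALY SD of 0.06 the half-width stays at 0.031 or more, well above 0.0115. The primary outcome is unaffected. This should be changed, but nothing else in the plan depends on it.

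**What to change.** Move the pre-fracture EQ-5D-5L items into the questionnaire patients already receive at T0, and state that they are completed before allocation is known. Keep the post-fracture items at T1.

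In the cost-effectiveness section, state that incremental QALYs will be estimated by regressing each patient's QALY on arm and pre-fracture utility. The regression is refitted in every bootstrap replicate, with cost and QALY resampled together per patient, and the adjusted difference is used in the ICER, the plane and the acceptability curve. Report the unadjusted result as a sensitivity analysis and label the cost-utility result exploratory.

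The cost is one shift in the schedule, one covariate and a few sentences in the plan. Two limits remain: the pre-fracture score is still recalled, since patients enter up to three weeks after injury, and the interval at 30 patients stays wide.
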